## Addiction and Behavior Related to Menthol Cigarette Substitutes

currently active (have not completed all study visits) in the study. If a participant is ineligible for the study at the time of screening, the participant can be reassessed at a later time to determine if they are now eligible i.e. A participant meets all other eligibility criteria, but is not eligible because they are currently pregnant or breastfeeding. The participant can submit a new screener after they are no longer pregnant or breastfeeding and can be reassessed for eligibility. Reassessment for eligibility will vary based on previous ineligibility criteria and will be determined on a participant by participant basis.

Participants' eligibility will be determined over the phone or via REDCap's online screener. Those who are eligible and willing to participate will be invited to sign an informed consent and complete their baseline visit in a private participant room at the Ohio State University. All participants will be given adequate time to review the informed consent with a trained research staff to help answer any questions that may arise during the consent process. Additionally, a copy of the informed consent will be given to all participants. A pregnancy test will be completed at the initial visit as well as before starting all the in-lab visits to ensure that the participant is not pregnant.

**Retention:** All participants will receive \$50 per completed in-laboratory session, \$7 for parking (when applicable), \$50 bonus for completing all sessions (up to \$335), and up to \$30 for completing daily diaries over the two week ad-lib and observational use periods (\$30 for 12 more diaries completed, \$25 for 11 diaries completed, \$20 for 9-10 diaries completed, \$15 for 7-8 diaries completed and \$0 for 1-6 diaries completed) for a total up to \$365. Consistent with our previous studies, payments will be made using the Greenphire ClinCard to increase accountability and facilitate ease of payment. We will also facilitate study calls/visits by offering evening and weekend appointments as well as additional retention strategies (e.g., multiple sources of contact, reminder calls/texts/emails). Participants will receive reminder calls in addition to email or text reminders. Reminders will be sent by text or email based on a participant's preferred method of contact.

**Study Products:** [*Mentholated pipe tobacco in a roll-your-own cigarette tube (mRYO), menthol filtered little cigars (mFLC), and non-menthol cigarettes (nmC) were chosen as plausible menthol cigarette substitutes that are currently available on the commercial market.*] To produce the mRYO product, study staff will inject 1 gram of menthol OHM pipe tobacco ([www.smokersoutletonline.com/ohm-pipe-tobacco-1-lb.html](http://www.smokersoutletonline.com/ohm-pipe-tobacco-1-lb.html)) into manufactured Hot Rod King (84 mm; [www.smokersoutletonline.com/hot-rod-tubes.html](http://www.smokersoutletonline.com/hot-rod-tubes.html)) tubes using an electric rolling machine, as described in online user forums. The menthol filtered cigar will be Cheyenne ([Cheyennecigars.com](http://Cheyennecigars.com)) Seneca ([senecacigars.com](http://senecacigars.com)). All products (mFLC, mRYO, nmC) will be provided to participants in plain boxes without brand or identifying information for the in-lab and *ad libitum* sessions; the box will include a study product ID number sticker for tracking purposes. Brand or identifying information may be present on the actual product.

### Detailed Study Procedures

**UBMC and Study Product Lab Sessions (Phase 1):** Upon arrival at the lab, 12-hr tobacco abstinence will be assessed via self-report and confirmed with exhaled carbon monoxide testing ( $eCO \leq 10\text{ppm}$ ). Pregnancy exclusion will also be confirmed with a urine test; and breath alcohol concentration (BrAC) tests will ensure  $BrAC < .01$ . Participants will not be allowed to eat or drink (other than water) during the session. Participants will be instructed to smoke one UBMC or study product *ad libitum* to completion through a puff topography device.  $eCO$  will be collected immediately pre- and post-smoking. Measures of subjective effects (see Table 1) will be collected immediately before the onset of puffing and at 1-min, 15-min, 30-min, 60-min, and 90-min after completion of the cigarette. The Cigarette Purchase Task will also be completed during the lab sessions. Sessions will last

## Addiction and Behavior Related to Menthol Cigarette Substitutes

approximately 2 hours each. During this period, participants will complete one week of daily diaries to assess their usage of UBMC.

Preferred Study Product *Ad libitum*-Observational Use Period (Phase 2): During the preferred study product observational use period, participants will be provided products at no cost. Study products will be provided in a 1.2 to 1 ratio based on self-reported use at the time of screening. This slight over appropriation helps to ensure that participants have enough study product available so to not artificially limit use, while also not oversupplying and potentially artificially increasing use beyond what would be usual. Participants will be instructed to completely switch and exclusively use the study product during the 1-week time period. During this period, participants will complete one week of daily diaries. If the participant has not responded after 3 prompts, the assessment will be recorded as missed.

Final Lab Session – Simulated Menthol Cigarette Ban Using a Progressive Ratio Task (Phase 3): Following the one-week use period, participants will come to the lab following 12-hr nicotine abstinence confirmed by eCO. To simulate the effect that restricting menthol in cigarettes would have on increasing (or not) preference for other alternative menthol substitutes, participants will complete a 90-minute concurrent choice task with differential cost (effort) required to earn 2 puffs from their UBMC (10 clicks increasing to 7200 ) versus their preferred study product (always 10 clicks) from Phase 2. This session will last approximately 3 hours.

### Protocol Adherence and Quality Control

#### **Data Management**

All data collection will follow HIPAA guidelines. Data will be collected directly from the participant by a research assistant. Data will include participant responses to computer-based and phone-based survey Questionnaires, as well as exhaled carbon monoxide samples and progressive ratio task and puff topography readouts.

Access to Identifiable Information and Data Storage: Only research assistants who have completed training in the ethical conduct of research and the study MPIs (Drs. [name] and [name]) will have access to individually identifiable private information about human subjects. All data will be treated as confidential and will never be stored or reported in association with identifying information. Hard copies of signed informed consent and the patients cover sheet which includes contact information will be stored in locked filing cabinets separate from participants' study-related data. A common identification number will link identifiable forms (consent forms and contact information) and study-related data. Computer entered data will be de-identified and password-protected.

#### **Quality Assurance**

All research staff will have completed Human Subjects and HIPAA training. Standard operating procedures (SOP) have been developed for similar studies run by our lab; we will spend the first month developing the SOP for this protocol. All staff will be trained to ensure adherence to the SOP. As is standard practice for our team's current studies, each visit will have its own checklist of specific measures to be completed and the order in which they are to be administered. On-site personnel will meet face-to-face weekly throughout the study, with [name] joining all weekly meetings via Skype.

## Addiction and Behavior Related to Menthol Cigarette Substitutes

### 3. Measures

Questionnaire data will be collected over the phone or in-person by a trained research assistant and data will be entered into a secured and encrypted database using REDCap. See Table 1 for timing of measures. Sociodemographic measures will assess participant age, sex, marital status, ethnicity, employment status, occupation, years of education, and socioeconomic status. Tobacco use history will assess years of smoking, age of smoking onset, average number of cigarettes per day, number and recency of previous 24-hour quit attempts, number of smokers in the household, prior use of nicotine replacement therapy and other stop smoking medications, and history of receiving smoking cessation counseling. It will also assess tobacco type, brand, frequency, quantity, and duration of use all of nicotine/tobacco products including cigars, cigarillos, little cigars, pipe tobacco, chewing tobacco, snuff, snus, EC/vape/mod/APV/e-hookah, combusted tobacco hookah, and dissolvable tobacco. Cigarette Dependence will be measured with the 12-item Cigarette Dependence Scale. Exhaled carbon monoxide will be assessed at the start of each study visit. Abuse liability of products will be measured across several domains 1) smoking puff topography, 2) subjective effects, 3) behavioral economic choice tasks, and 4) craving for and suppression of craving and withdrawal. Smoking puff topography will be measured with CReSS Pocket Topography Device by Borgwaldt. The device uses a pressure transducer integrated into a plastic cigarette holder to produce measures of puff count, puff duration, inter-puff-interval, puff flow rate, average puff volume, and total puff volume. Puff topography is a validated and sensitive behavioral measure of abuse liability, is highly stable and associated with level of dependence and predicts level of exposure to harmful tobacco-related toxicants. An adapted version of the Drug Effects/Liking Questionnaire will assess the desire and liking of UBMC and all three study products, positive and negative effects (i.e., side effects), and perceived strength and effectiveness. [The modified Cigarette Evaluation Questionnaire (mCEQ) will also assess subjective responses to cigarettes (e.g., reward, satisfaction).] The Cigarette Purchase Task will ask participants how much they would be willing to pay (ranging from 0¢ to \$1,120) to smoke each product. Given that the study products will look similar to cigarettes, we will retain the original language (e.g., “1 cigarette”) in the purchase task. [Willingness to spend more will indicate greater abuse liability.] Smoking urges/craving will be measured using the Tiffany-Drobes Questionnaire of Smoking Urges: Brief Form. This is a 10-item measure where participants rate smoking-related items (“All I want right now is a cigarette.”) on a 7-point Likert scale ranging from ‘strongly agree’ to ‘strongly disagree’. Similar to previous studies, we will collapse the items into two previously identified factors (Factor 1: strong desire and intention to smoke; Factor 2: anticipation of relief from withdrawal symptoms). Nicotine withdrawal will be assessed using the empirically validated 15-item version of the Minnesota Nicotine Withdrawal Scale. This measure assesses smoking craving, anger/irritability, anxiety, depressed mood, restlessness/difficulty concentrating, increased appetite, sleep problems, and somatic symptoms (nausea, constipation, sore throat, dizziness, coughing). [Subjective effects (daily diary) of the Phase 2 substitute product will be derived from daily diaries assessing product satisfaction and pleasure.] [Substitutability of products will be assessed using a Cross-Price Task, a Progressive Ratio (PR) Task and daily diaries. A Cross-Price Task in Phases 1 and 3 will estimate substitutability of the study product for the UBMC. Participants will be asked how many study products and UBMCs they would consume when the price of the study product is fixed at \$1 and the UBMC prices escalate. The data are then fit to an exponential equation that indicates whether the fixed-price product substitutes for the primary product, and the degree of substitution. Cross price elasticity (CPE) for each study product compared to UBMC  $> 0.2$  indicates substitution,  $CPE <$

**Addiction and Behavior Related to Menthol Cigarette Substitutes**

-0.2 indicates complementarity, and CPE between -0.2 and 0.2 indicate independence of the two products. Consistent with previous studies conducted by [name], the PR task will simulate the effect that restricting menthol in cigarettes would have on increasing (or not) preference for other alternative menthol substitutes. Participants will complete a 90-minute concurrent choice task with differential cost (effort) required to earn the reinforcement (2 puffs) from their UBMC and the study product (mFLC,mRYO or nmC). Puffs from the study product can be earned by clicking a computer mouse 10 times on a picture of the study product, but to earn two puffs of the UBMC, they will be required to make escalating response requirements (computer mouse clicks) according to the following schedule: 10, 160, 320, 640, 1280, 2400, 3600, 4800, 6000, 7200. A maximum of 10 reinforcers (20 puffs) per session will be allowed. The proportion of reinforcers earned is considered to provide an index of the strength of the reinforcing effects of the product. Participants will be informed of the differential sequence between products and instructed that the sessions are 3 hours in length no matter how much or how little they respond. Daily diaries will assess UBMC/study product smoked per day, product satisfaction and pleasure (see Table 1 for specific daily diary measures). [Substitution assessed via use behavior during Phase 2 will be operationalized as the ratio of study product to UBMC used, with a ratio > 0 indicating any substitution and a ratio > 1 indicating substitution of study product for the UBMC at least 50% of the time.]

Table 1. Measures

Measures	Phase 1:			Phase 2:	Phase 3:
	3 in-lab visits			1-week	Final Lab
	Visit 1	Visit 2	Visit 3	Visit 4	Visit 5
Background Measures					
Exhaled CO Abstinence verification	X	X	X	X	X
Pregnancy Test	X	X	X	X	X
Exhaled carbon monoxide	X	X	X	X	X
Breath Alcohol Concentration (BrAC)	X	X	X	X	X
Taste testing strips (PROP)	X				
Sociodemographic measures	X				
Cigarettes Use/Tobacco Use Hx (EDSHC)	X				
Menthol Subscales	X				
Readiness Rulers	X				
Product Use Status	X				
Product Use Detailed Assessment	X				

Addiction and Behavior Related to Menthol Cigarette Substitutes

Fagerstrom	X				
Abuse liability					
Smoking topography	X	X	X	X	
Drug Effects/Liking Questionnaire	X	X	X	X	X
Modified Cigarette Evaluation Questionnaire (mCEQ)	X	X	X	X	X
Tiffany-Drobes Questionnaire of Smoking Urges: Brief Form (modified)	X	X	X	X	X
MNWS	X	X	X	X	X
Cigarette Purchase Task	X	X	X	X	X
Subjective effects (Daily Diary)	X			X	
Substitutability					
Cross Price Elasticity Task		X	X	X	X
Progressive ratio task (UBMC vs. study product - computer task)					X
Record final product selected				X	
Use behavior (Daily Diary)	X			X	
Daily diary					
· # Study products smoked				X	
· # Non-study products smoked	X			X	
· Other tobacco use	X			X	
Modified Cigarette Evaluation Questionnaire (mCEQ)	X			X	
Drug Effects/Liking Questionnaire	X			X	
Behavioral Intentions				X	
Tiffany-Drobes Questionnaire of Smoking Urges: Brief Form (modified)	X			X	
MNWS	X			X	

Addiction and Behavior Related to Menthol Cigarette Substitutes

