### Study Weaknesses and Design Considerations

What if none of the study products substitute for menthol cigarettes? Industry evidence has shown menthol cigarette smokers prefer their own brand among other menthol brands. Therefore, it is possible that our study products will not be sufficiently satisfying to substitute for UBMCs. [To address this, we have included a Newport non-menthol cigarette as one of the substitutes in Phase 1 and allow participants to choose their preferred study product for the extended observation period in Phase 2. To reduce the likelihood of a null finding, we include multiple measures of substitution, including use behavior via daily diary (Phase 2) and a progressive ratio (PR) task comparing the study product to the UBMC in Phase 3.] The PR task is a sensitive measure to assess changes in substitutability of the study product. Lack of significant findings, however, will also be informative to FDA in determining whether or how other non-cigarette products should be included under a proposed ban on menthol in cigarettes.

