### 2. Data Analytic Plan

Statistical analyses will be performed using SAS 9.4 and an alpha of .05. Background measures will be summarized by product (UBMC, mFLC, mRYO, nmC), as appropriate. Continuous variables will be presented as mean  $\pm$  SD; categorical variables will be presented as counts and proportions. We will apply a transformation to normalize the distribution and stabilize the variance of the residuals where appropriate.

Hypotheses 1a and 1c: We will use Repeated Measures Analysis of Variance with Tukey-adjustment to examine differences between the alternatives and the UBMC in abuse liability assessed at each product lab session. Assuming statistically significant product differences, this post-hoc test will allow us to not only compare each product to the UBMC, but will also allow comparison of the alternative products with each other. Because product introduction in Phase 1 will be randomized using a Latin Square, a fixed effect for session and a random effect for sequence will be included in all analyses.

Hypothesis 2a: Product preference will be examined using a Chi-Square Test, comparing the proportions of participants choosing each alternate product for further use.

Hypothesis 2b: We will examine the trajectory of use behavior outcomes using Linear Mixed Model (LMM) regression analysis. We will employ a random intercept or slope parameter, as appropriate, and model the covariance structure for the repeated outcome measures, while accounting for potential confounders, including gender and baseline cigarettes/day.

Hypothesis 2c: This aim will be analyzed as a Chi-Square Test of Goodness of Fit to test the proportion of use compared to 80%.

Hypothesis 3: We will examine whether differences in product characteristics and changes in perceived effects collected via daily diary are associated with increased substitution of the alternate product over the seven-day period using generalized LMM regression analysis, similar to that outlined in H2b.

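### Cross-price elasticity labels (substitute, complement, independent) depend only on which side of ±0.2 the estimate falls, so an imprecise estimate can be read as independence

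*Combined protocol and SAP*

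**What the plan says.** Section D.3 (Measures) names three ways of assessing substitutability: the cross-price task, the progressive ratio task and the daily diaries. On the first it says: "A Cross-Price Task in Phases 1 and 3 will estimate substitutability of the study product for the UBMC". Participants state how much of each product they would consume while the study product's price stays fixed and the usual-brand price rises. An exponential equation fitted to these answers is meant to show "whether the fixed-price product substitutes for the primary product, and the degree of substitution".

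The cut-offs follow. The quantity classified is "Cross price elasticity (CPE) for each study product compared to UBMC". A value above 0.2 is read as substitution and a value below minus 0.2 as complementarity, and "CPE between -0.2 and 0.2 indicate independence of the two products". No standard error, interval, test or inconclusive outcome goes with these cut-offs.

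Section E.2 (Data Analytic Plan) opens with a general statement, "Statistical analyses will be performed using SAS 9.4 and an alpha of .05", and then gives analyses for H1a and H1c, H2a, H2b, H2c, H3 and moderation by age. None mentions CPE. Section E.1 (Power Analysis) covers abuse liability measures and Phase 2 use. The only confidence interval in the documents is in E.1 and concerns the Phase 2 use proportion.

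**The concern.** Calling two products independent is an equivalence claim with a margin of ±0.2. It should require data precise enough to exclude values outside the margin. Under the cut-offs as written, a point estimate inside the band is sufficient, however wide its interval. Lack of precision can then be reported as evidence that a product does not substitute for menthol cigarettes. The substitution label has the mirror problem: an estimate just above 0.2 earns it even if its interval includes values well below 0.2.

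Substitutability is the subject of Aim 2, and the cross-price task is one of its three measures. A misplaced independent label for one product could colour how that product is described, even though no formal test depends on it.

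**Working it through.** The plan gives no SD, standard error, power or error rate for CPE, so there is no figure of its own to reproduce. The check asks how the labels would behave over a range of assumed precision.

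**Inputs**
- Margin: ±0.2 (D.3).
- n = 80: the number expected to complete (Recruitment Feasibility and Retention; also used in E.1).
- Between-participant SD of CPE: not in the documents. Assumed 0.5 to 1.0, with 0.2 as a favourable case.
- Unit: the mean of participants' CPEs for one product. This is an assumption, because D.3 does not say whether the label applies to individual fits, their mean or a pooled curve. Its wording points to the product level.
- Estimate approximately normal around the true value, with SE = SD/√n.

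**Standard errors at n = 80 (√80 = 8.944)**
- SD 0.2: 0.0224
- SD 0.5: 0.0559
- SD 1.0: 0.1118

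**One estimate.** With an estimate of 0.15 and SE 0.112, the 95% interval is 0.15 ± 1.96 × 0.112 = 0.15 ± 0.22, or -0.07 to 0.37. This covers both no relation and clear substitution. The plan's cut-offs read it as independent.

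**Rule as written, true CPE 0.30.** P(independent) = Φ((0.2 - 0.3)/SE) - Φ((-0.2 - 0.3)/SE).
- SD 0.2: Φ(-4.47), below 0.1%
- SD 0.5: Φ(-1.79) = 3.7%
- SD 1.0: Φ(-0.89) = 18.6%

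The second term is negligible in all three cases.

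**Smaller groups.** If the Phase 3 task covers only each participant's preferred product, which D.3 does not state, the groups will be smaller. An even three-way split gives about 80/3 ≈ 27 per product, SE 0.096 to 0.192 for SD 0.5 to 1.0, and the same probability is 14.9% to 29.7%.

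**Interval-based rule, n = 80.** A product is a substitute if the lower 95% limit exceeds 0.2, with probability Φ((true - 0.2)/SE - 1.96). It is independent if the 90% interval lies inside ±0.2, which at a true CPE of 0 has probability 2Φ((0.2 - 1.645 × SE)/SE) - 1.

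| True CPE | Label | SD 0.5 | SD 1.0 |
|---|---|---|---|
| 0 | independent | 95% | 11% |
| 0.30 | substitute | 43% | 14% |
| 0.40 | substitute | 95% | 43% |

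The independent label cannot be reached at all once SE exceeds 0.2/1.645 = 0.122, that is, once SD exceeds about 1.09 at n = 80.

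**The case against.** The cut-offs sit in a measures section, carry a citation and say what values indicate. They can be read as a guide to the scale, since D.3 also promises an estimate of the degree of substitution. Nothing forbids an interval, and E.2 sets a general alpha. This lowers the weight of the point but does not remove it: a cited margin fixes where the limits lie, not how sure one must be of crossing them, and no analysis in E.2 tests CPE against them.

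The objections to stronger readings do stand:
- A reader might infer that a powered or primary conclusion is at risk. The documents do not support this. H2a to H2c rest on product choice, diary use and a proportion, and E.1 does not use CPE.
- A reader might connect the label to the statement that "Lack of significant findings, however, will also be informative to FDA". That paragraph, in Study Weaknesses and Design Considerations, names the diary and the progressive ratio task and speaks of the study's results in general. Nor do the documents say that the CPE label decides which products a ban should cover; they say only that the findings may inform rulemaking.
- A reader might take the 50% chance of either label at a true CPE of exactly 0.20 as the main fault. That holds for any cut-off with a symmetric, unbiased estimator, and at that value neither label is a serious error.
- All other error rates rest on an assumed SD. If labels were given to individual participants, SD/√n would not describe the labelling error.

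**Conclusion.** The point holds as a gap in how CPE results will be interpreted. Followed as written, the plan would call an imprecise estimate inside ±0.2 independent, with no interval or inconclusive category to prevent it. How often this would happen is unknown. With 80 participants and a true CPE of 0.30, the illustrative rate is 4% to 19% for an SD of 0.5 to 1.0 and negligible for an SD near 0.2. These figures assume product-level means and a normal approximation; elasticities from nonlinear fits may be skewed. CPE is in effect a secondary measure of substitutability, so the consequence is a possible misdescription of individual products, not a failure of a planned hypothesis test.

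**What to change.** In D.3 and E.2:
- State that the label applies to the product-level CPE, and how that CPE is obtained.
- Report each product's CPE with a 95% confidence interval, with the participant as the unit or by a participant-level bootstrap.
- Keep ±0.2 as the margin.
- Use the independent label only when the 90% interval lies wholly within ±0.2 (two one-sided tests at 5%).
- Use the substitute label only when the lower 95% limit is above 0.2, and the complement label only when the upper 95% limit is below minus 0.2.
- Otherwise give the estimate and interval and call the result inconclusive.

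This needs plan wording and a few lines of code, and no new data. The real cost is fewer firm labels. At the upper assumed SD of 1.0, many results would be inconclusive even with all 80 participants, as the table in the working shows, and smaller Phase 3 groups would fare worse. If that is thought too strict, the minimum is to report every CPE with its interval and to claim neither independence nor substitution when the interval crosses a limit.

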## Addiction and Behavior Related to Menthol Cigarette Substitutes

*craving reduction, improved mood with use, and ease of use [on daily diaries, will report the greatest substitution of study product for UBMC.]*

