**Figure 2. Study Overview**

in-person lab visits. At the beginning of each visit, pregnancy tests will be completed to ensure that the participant is not pregnant. During visit 1, participants will complete a PROP taste test to measure a participants' perceived intensity to taste. In *Phase 1*, utilizing a randomized crossover design, participants will complete [4 smoking sessions,] each session smoking a different product examining each [participants' puff topography while sampling the product, the product's ability to suppress nicotine craving/withdrawal, and the product's demand indices. Products will include participants' usual brand menthol cigarette (UBMC) as well as 3 commercially-available alternatives, including an mFLC, a pre-assembled mRYO product (menthol tobacco + menthol tube), and an nmC.] All sessions will occur following 12-hrs of nicotine abstinence and be separated by 48-hrs. Participants will complete daily diaries for one-week during this period to more accurately assess current use of their UBMC. In *Phase 2*, participants will [select their preferred study product from Phase 1] and be instructed to completely substitute the product for their UBMC for one week. Participants will complete daily diaries during this period to more accurately assess degree of substitution and perceived effects in real-time. In *Phase 3*, participants will complete a final in-lab visit to assess the substitutability of their preferred product, under simulated ban conditions using a progressive ratio task. In all phases, multiple domains of abuse liability will be assessed, including product administration (in-lab puff topography and daily diary self-report measures), product liking and craving and withdrawal suppression (in-lab and daily diary self-report), and hypothetical purchase tasks to simulate demand.

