## Addiction and Behavior Related to Menthol Cigarette Substitutes

12 hours of overnight tobacco abstinence, biochemically verified by exhaled carbon monoxide ( $eCO \leq 10\text{ppm}$ ). Sessions will be separated by a standard 48-hour washout period. Participants will smoke one cigarette ad libitum and a puff topography device will discretely record smoking behavior throughout the session, including puff duration, number of puffs, puff volume, and time between puffs.  $eCO$ , and self-report measures of craving and withdrawal will be recorded immediately before and at several times after the smoking session. Self-report measures of abuse liability will also be completed during the sessions. During the preferred study product observational use period, participants will be provided a weeks' worth of a potential menthol substitute at no cost. Consistent with our previous switching studies, study products will be provided in a 1.2 to 1 ratio based on self-reported use at the time of screening. This slight over appropriation helps to ensure that participants have enough study product available so to not artificially limit use, while also not oversupplying and potentially artificially increasing use behind what would be usual. Participants will be instructed to completely switch and exclusively use the study product during the 1-week time period. During this period, participants will complete daily diary once a day. Following the one-week use period, participants will come to the lab following 12-hr nicotine abstinence confirmed by  $eCO$ . To simulate the effect that restricting menthol in cigarettes would have on increasing (or not) preference for other alternative menthol substitutes, participants will complete a 90-minute concurrent choice task with differential cost (effort) required to earn 2 puffs from their UBMC (10 clicks increasing to 7200) versus their preferred study product (always 10 clicks) from Phase 2. . This session will last approximately 3 hours.

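### The Phase 2 substitution ratio (study product divided by UBMC) has no value when no UBMC is smoked, which is the instructed behavior; H3 is the analysis most exposed

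*Combined protocol and SAP*

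**What the plan says.** Section D.3 (Measures) defines substitution from Phase 2 use behavior as "the ratio of study product to UBMC used, with a ratio > 0 indicating any substitution". A second cut-off follows there: values above 1 are read as the study product having replaced the UBMC on half or more of occasions. The counts come from the diary: "Daily diaries will assess UBMC/study product smoked per day". Table 1 lists the diary items as study products smoked, "Non-study products smoked", and other tobacco use.

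The Phase 2 instruction appears twice in section D.2, under Study Procedures and under Detailed Study Procedures: "Participants will be instructed to completely switch and exclusively use the study product during the 1-week time period". Product is free and supplied at 1.2 times self-reported use, so complete switching is feasible.

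Three places ask for a degree of substitution rather than a yes/no answer:
- Section D.1 (Design Overview) says the Phase 2 diaries are kept "to more accurately assess degree of substitution and perceived effects in real-time".
- H3 in section A (Specific Aims) predicts which participants "will report the greatest substitution of study product for UBMC".
- Section E.2 (Data Analytic Plan) tests whether product characteristics and perceived effects are "associated with increased substitution of the alternate product over the seven-day period using generalized LMM regression analysis". It does not name the outcome variable, distribution or link.

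**The concern.** The denominator is the UBMC count. A participant who does what the protocol asks has a count of zero, so the measure fails at the outcome Phase 2 is set up to observe. Neither D.3 nor E.2 says what to do then, or whether the ratio is formed per day or per week.

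If substitution is analyzed as a quantity, the analyst has two ad hoc options. One is to drop the undefined days, which removes observations because of their outcome and cuts off the top of the range. The other is to add a constant to the denominator, which makes the result depend on that constant. Either choice would be made after the data are seen. At stake is the estimate for H3, the only hypothesis under Aim 3.

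**Working it through.** **1. What the ratio means.** Let S be the study-product count, U the UBMC count and r = S/U. The share is S/(S+U) = r/(1+r).

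| S | U | Ratio | Share |
|---|---|---|---|
| 0 | 10 | 0 | 0 |
| 5 | 5 | 1 | 0.50 |
| 9 | 1 | 9 | 0.90 |
| 10 | 0 | undefined | 1.00 |

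The plan's cut-off reproduces: r > 1 is the same as a share above 0.5. The one discrepancy is at an exact tie (r = 1), which the D.3 wording includes and its inequality excludes. Close to full substitution the ratio is also unbounded: 9/1 = 9, 19/1 = 19.

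**2. Do existing rules cover U = 0?** The available-data route in section E.3 requires under 5% missing and missingness at random, but these values are undefined because of the outcome. Its imputation route has no finite true ratio to recover. The general transformation sentence in E.2 does not resolve division by zero.

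**3. How often would U = 0 occur?** Under full compliance, always. For partial compliance, assume each of N cigarettes per day is independently the study product with probability s. Then P(U = 0) is s^N for a day and s^(7N) for a week. N = 5 is the entry minimum in D.2; the other inputs are assumptions.

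| s | N = 5 | N = 10 | N = 15 |
|---|---|---|---|
| 0.80, day | 0.328 | 0.107 | 0.035 |
| 0.95, day | 0.774 | 0.599 | 0.463 |
| 0.95, week | 0.166 | 0.028 | 0.005 |

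At s = 0.80 and N = 5 the weekly figure is 0.80^35 = 0.0004. Under independence the problem is therefore mainly at day level. For a person who switches exclusively, the weekly probability is 1.

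**4. Effect on H3 (simulation, all settings assumed).** 600 replicates of 80 people over 7 days, with S ~ Bin(N, p) and logit p = μ + 0.5x + u. Here u ~ N(0,1), and x has variance 1, half between and half within persons. A pooled binomial logit of S/(S+U) on x was fitted to all days and again to days with U > 0. The all-day slope is below 0.5 because the pooled model is population-averaged.

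| Mean share | N | Days lost | Slope, all days | Slope, U > 0 | Change |
|---|---|---|---|---|---|
| 0.77 | 5 | 38.8% | 0.434 | 0.223 | −49% |
| 0.77 | 10 | 22.1% | 0.432 | 0.300 | −31% |
| 0.77 | 15 | 14.5% | 0.427 | 0.333 | −22% |
| 0.50 | 15 | 1.8% | 0.420 | 0.396 | −6% |

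At a mean share of 0.77, the proportion of people with U = 0 all week was 4.0%, 1.2% and 0.5% at N = 5, 10 and 15.

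The ratio was also tested directly. At N = 5 its correlation with x on defined days was 0.22, against 0.30 for the share on all days. Slopes for the log ratio ran from 0.26 to 0.84 depending on the offset added.

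A different model (10 cigarettes per day; the highest-substituting 10%, 30% or 50% switch fully) also showed attenuation. The satisfaction slope fell from 0.143 to 0.115, 0.159 to 0.102 and 0.162 to 0.081.

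**5. H2c, illustration only.** Suppose H2c is tested on Phase 2 use and a fraction f of complete switchers is dropped from a true 80%. The observed proportion is q = (0.8 − f)/(1 − f), with n = 80(1 − f) and z = (q − 0.8)/√(0.16/n).
- f = 0.04: q = 0.76/0.96 = 0.792, z = −0.18
- f = 0.10: q = 0.70/0.90 = 0.778, z = −0.47
- f = 0.20: q = 0.60/0.80 = 0.750, z = −1.00

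The last two lie outside E.3's under-5% condition and are a worst case. If complete switchers are scored as majority users, the bias is zero.

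**The case against.** D.3 uses the ratio only through two cut-offs, and anyone with S > 0 and U = 0 plainly exceeds both. The H3 harm needs several choices the plan does not state: that H3 uses this ratio, per day, as a quantity, and that undefined days are dropped or offset. A generalized mixed model could equally take a binary outcome or the daily study-product count, and neither needs division. The slope simulation fits the share and then deletes days, which nobody using the share would do. It also reports slopes rather than tests. With person-clustered standard errors in the same setup, power with all days versus U > 0 days was 99.5% versus 90.5% at 5 per day, 100% versus 98.5% at 10, and 100% versus 100% at 15. Finally, Table 1 has its own row for other tobacco, so the non-study item probably does capture UBMC.

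Much of this stands. The classification is safe, H3's outcome is unnamed, and under these assumptions the directional test usually survives. Smaller true effects could lose more power; that was not examined.

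Two parts do not remove the point. D.3 makes the ratio the operational form of substitution through Phase 2 use behavior, so the use-behavior row in Table 1 leads back to it. And the direct test of the ratio shows both the loss of association and the dependence on the offset.

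**Conclusion.** The concern holds. That the measure is undefined under the instructed behavior is certain from the text, and nothing in E.2 or E.3 repairs it. The consequence is conditional: it arises if substitution is analyzed daily or as a quantity, which H3 most naturally implies but E.2 does not state.

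Under the assumed compliance rates, dropping undefined days weakens the H3 slope by 6% to 49%. The loss is greatest among light smokers with high substitution. The bias ran toward zero in every scenario examined, and it affects the estimate more than the significance test. The −49% figure assumes everyone smokes exactly the entry minimum.

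The participant-level majority classification is unaffected once complete switchers are scored as substituting. The cross-price and progressive ratio measures do not use this ratio. H2c is touched only if it is tested on Phase 2 use, as E.1 (Power Analysis) suggests, rather than under the simulated ban named in section A, and only if complete switchers are dropped. The definition should be corrected before analysis.

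**What to change.** - In D.3, define substitution as study product / (study product + UBMC). Any substitution is a share above 0; complete substitution is a share of 1.
- For the participant-level endpoint, sum both counts over completed Phase 2 diary days and report how many days were completed. Missed diaries are not zeros.
- For H3 in E.2, name the outcome: the daily share, modeled as a binomial proportion in the generalized mixed model already planned. Days with neither product used contribute nothing and are counted in the report.
- Use one majority cut-off in section A, D.3 and E.1, so that exact ties are treated the same way throughout.
- Confirm that the diary records UBMC as its own count, since D.3 implies this and Table 1 does not show it.
- State whether H2c is tested on this measure or on the Phase 3 task.

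The cost is a few sentences in D.3, E.1 and E.2, with section A aligned on the cut-off, and no new visits. No new data are needed unless the diary pools UBMC with other non-study products, in which case one item must be split.
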